It is possible that irAEs other than those listed in the guidance document may be observed in subjects receiving pembrolizumab; therefore, all AEs of unknown etiology associated with drug exposure should be evaluated to determine if it is possibly immune related. This is meant to be a general guidance; therefore, recommendations in the current document might not be all inclusive. As such Investigators are encouraged to contact a Merck Clinical Monitor as needed to discuss cases that warrant separate discussion outside of the scope of current guidelines. Permanent discontinuation of pembrolizumab due to irAE may be subject of discussion between the SPONSOR and treating Investigator. The general approach to handling irAEs can be found in Appendix I.

All AEs are to be graded according to National Cancer Institute Common Terminology Criteria for Adverse Events (NCI CTCAE), version 4.0 (<http://ctep.cancer.gov>).

If an irAE does not resolve or improve to \leq Grade 1 (or to Grade 2 for ALT or AST) within 12 weeks from the start of grade 2 toxicity (or start of grade 3 toxicity for AST, ALT) study therapy discontinuation should be considered at the PI discretion or after discussion with a Merck Clinical Director.

Infusion Reactions

Infusion reactions have been reported with pembrolizumab at a rate of 2.5%; these were generally Grade 1 and 2 and the majority were considered related by the Investigator. One event of Grade 4 anaphylaxis has been reported. Infusion reactions may present as allergic reaction, serum sickness, infusion reaction, cytokine release syndrome, or anaphylaxis. Mild infusion reactions can generally be treated with interruption of the infusion and medical intervention including IV fluids, antihistamines, nonsteroidal anti-inflammatory drugs, acetaminophen, and narcotics as needed. More severe or life threatening reactions may require pressors, corticosteroids, and epinephrine. Pembrolizumab therapy should not be redosed in these more severe cases.

Stevens-Johnson Syndrome (SJS) and Toxic Epidermal Necrolysis (TEN)

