Colitis (including microscopic colitis) occurred in 4 (1%) of 411 patients, including Grade 2 or 3 cases in 1 (0.2%) and 2 (0.5%) patients, respectively, receiving KEYTRUDA in Trial 1. The median time to onset of colitis was 6.5 months (range 2.3-9.8). The median duration was 2.6 months (range 0.6 weeks-3.6 months). All three patients with Grade 2 or 3 colitis were treated with high-dose corticosteroids (greater than or equal to 40 mg prednisone or equivalent per day) with a median initial dose of 70 mg/day of prednisone or equivalent; the median duration of initial treatment was 7 days (range 4-41), followed by a corticosteroid taper. One patient (0.2%) required permanent discontinuation of KEYTRUDA due to colitis. All four patients with colitis experienced complete resolution of the event. Monitor patients for signs and symptoms of colitis. Administer corticosteroids for Grade 2 or greater colitis. Withhold KEYTRUDA for moderate (Grade 2) or severe (Grade 3) colitis, and permanently discontinue KEYTRUDA for life-threatening (Grade 4) colitis.

Immune-Mediated Hepatitis

Hepatitis (including autoimmune hepatitis) occurred in 2 (0.5%) of 411 patients, including a Grade 4 case in 1 (0.2%) patient, receiving KEYTRUDA in Trial 1. The time to onset was 22 days for the case of Grade 4 hepatitis which lasted 1.1 months. The patient with Grade 4 hepatitis permanently discontinued KEYTRUDA and was treated with high-dose (greater than or equal to 40 mg prednisone or equivalent per day) systemic corticosteroids followed by a corticosteroid taper. Both patients with hepatitis experienced complete resolution of the event.

Elevated transaminases and alkaline phosphatase may be seen during treatment. Treatment should be interrupted when transaminase or alkaline phosphatase increases are accompanied by Grade 3 total bilirubin, and/or Grade 3 coagulation tests (e.g., International Normalized Ratio [INR]), or if subjects are clinically symptomatic.

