Evaluation of subjects with elevated transaminases, bilirubins, and alkaline phosphatase should involve a workup to assess for infection (SBP or other), viral reactivation (if relevant), vascular thrombosis, biliary obstruction, possible hepatotoxic medications, tumor progression, alcohol toxicity, and effects of pembrolizumab. At baseline, all subjects should be assessed for HBsAg, HBsAb, anti-HBc antibody, HBeAg, and anti-HCV. As described above, a viral load <100 IU/mL is required for study entry, and with active HBV must have also been treated with antiviral therapy for ≥ 3 months before initiation of study treatment. Subjects with controlled HBV on therapy should stay on this same therapy throughout pembrolizumab treatment. Subjects who are positive for HBsAg or anti-HBc (but negative for HBsAg and HBV DNA), should be assessed for HBV viral load, HBsAg, HBsAb, anti-HBc antibody, HBeAg every 3 weeks, independent of treatment delays.

Subjects with chronic infection by hepatitis C virus (HCV) with successful treatment (defined as SVR12 or SVR24) may be included. HCV genotype should also be recorded at baseline. **Untreated HCV positive subjects are eligible, and if stable after 6 months on pembrolizumab, additional antiviral treatment for HCV may be considered per local standard of care.** Viral loads should be assessed for those with an underlying viral etiology q 3 weeks. They should also be checked if there is an elevation in ALT $> 3 \times$ baseline, a tenfold or greater increase in HBV or HCV DNA $>$ baseline, or an absolute increase in HBV or HCV DNA $> 10^5$ c/mL. If evidence of reactivation is present, the Sponsor should be consulted within 24 hours, and pembrolizumab treatment should be interrupted. A hepatology consult should be obtained.

- For **Grade 2** AST/ALT or alkaline phosphatase events (if normal or Grade 1 at baseline) and no other etiology is found, monitor liver function tests weekly.

- For **Grade 3-4** AST/ALT, alkaline phosphatase events if normal at baseline), or $>3\times$ baseline (if greater than $2\times$ ULN at baseline) and no other underlying etiology is found, consider treatment with intravenous corticosteroids for 24–48 hours. When improved to baseline (for those with levels $\geq 2\times$ ULN at baseline) or Grade 1 or less (for those with normal baseline values), a steroid taper should be started and continued over no less than 4 weeks.

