10.0 TREATMENT/ DOSE MODIFICATIONS

10.1 Unacceptable Toxicity

Causality for all adverse events should be assessed and if deemed attributable, attempts should be made toward proper attribution.

Drug-related grade 4 toxicities will require subject to discontinue all study treatment. Intolerable grade 2 and grade 3 toxicities should be managed as per dose modification guidelines listed in the table below. Pembrolizumab therapy may be continued providing the residual adverse events are within permissible ranges for pembrolizumab dosing.

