Pneumonitis	Grade 2	Withhold	Administer corticosteroids (initial dose of 1-2 mg/kg prednisone or equivalent) followed by taper	Monitor participants for signs and symptoms of pneumonitis Evaluate participants with suspected pneumonitis with radiographic imaging and initiate corticosteroid treatment Add prophylactic antibiotics for opportunistic infections
	Grade 3 or 4, or recurrent Grade 2	Permanently discontinue		
Diarrhea / Colitis	Grade 2 or 3	Withhold	Administer corticosteroids (initial dose of 1-2 mg/kg prednisone or equivalent) followed by taper	
 • Monitor participants for signs and symptoms of enterocolitis (ie, diarrhea, abdominal pain, blood or mucus in stool with or without fever) and of bowel perforation (ie, peritoneal signs and ileus). • Participants with \geq Grade 2 diarrhea suspecting colitis should consider GI consultation and performing endoscopy to rule out colitis. • Participants with diarrhea/colitis should be advised to drink liberal quantities of clear fluids. If sufficient oral fluid intake is not feasible, fluid and electrolytes should be substituted via IV

	Grade 4	Permanently discontinue		infusion.
AST / ALT elevation	3	Withhold	Administer corticosteroids (initial dose of 0.5- 1 mg/kg prednisone or equivalent) followed by taper	Monitor with liver function tests (consider weekly or more frequently until liver enzyme value returned to baseline or is stable
	4	Permanently discontinue --see exception below ²	Administer corticosteroids (initial dose of 1-2 mg/kg prednisone or equivalent) followed by taper	
Increased bilirubin	Grade 2	Withhold	Administer corticosteroids (initial dose of 0.5- 1 mg/kg prednisone or equivalent) followed by taper	Monitor with liver function tests (consider weekly or more frequently until liver enzyme value returned to baseline or is stable
	Grade 3 or 4	Permanently discontinue	Administer corticosteroids (initial dose of 1-2 mg/kg prednisone or equivalent) followed by taper	
Type 1 diabetes mellitus (T1DM) or Hyperglycemia	Newly onset T1DM or Grade 3 or 4 hyperglycemia associated with evidence of β -cell failure	Withhold	Initiate insulin replacement therapy for participants with T1DM Administer anti-hyperglycemic in participants with hyperglycemia	Monitor participants for hyperglycemia or other signs and symptoms of diabetes.

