
1. Withhold or permanently discontinue pembrolizumab is at the discretion of the investigator or treating physician.
 
2. For grade 3 liver toxicity with elevated AST and/or ALT. Since HCC patients may have grade 1-2 elevation of AST/ALT at baseline, if these patients have Grade 3 elevation of AST/ALT, hold therapy and resume treatment when AST/ALT return to baseline or Grade ≤1. The AST/ALT should return to baseline or < 5 x ULN within 12 weeks from start of grade 3, otherwise patient should be discontinued from study.
 
3. Patients with intolerable or persistent Grade 2 drug-related AE may hold study medication at physician discretion. Permanently discontinue study drug for persistent Grade 2 adverse reactions for which treatment with study drug has been held, that do not recover to Grade 0-1 within 12 weeks of the last dose.
 
NOTE: For participants with Grade 3 or 4 immune-related endocrinopathy where withhold of pembrolizumab is required, pembrolizumab may be resumed when AE resolves to ≤ Grade 2 and is controlled with hormonal replacement therapy or achieved metabolic control (in case of T1DM).
				

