- For **Grade 2 events**, treat with corticosteroids. When symptoms improve to Grade 1 or less, steroid taper should be started and continued over no less than 4 weeks.

Replacement of appropriate hormones may be required as the steroid dose is tapered.

- For **Grade 3-4** events, treat with an initial dose of IV corticosteroids followed by oral corticosteroids. When symptoms improve to Grade 1 or less, steroid taper should be started and continued over no less than 4 weeks. Replacement of appropriate hormones may be required as the steroid dose is tapered.
- **Hyperthyroidism or Hypothyroidism:**

Thyroid disorders can occur at any time during treatment. Monitor patients for changes in thyroid function (at the start of treatment, periodically during treatment, and as indicated based on clinical evaluation) and for clinical signs and symptoms of thyroid disorders.

 - **Grade 2** hyperthyroidism events (and **Grade 2-4** hypothyroidism):
 - In hyperthyroidism, non-selective beta-blockers (e.g. propranolol) are suggested as initial therapy.
 - In hypothyroidism, thyroid hormone replacement therapy, with levothyroxine or liothyronine, is indicated per standard of care.
 - **Grade 3-4** hyperthyroidism
 - Treat with an initial dose of IV corticosteroid followed by oral corticosteroids. When symptoms improve to Grade 1 or less, steroid taper should be started and continued over no less than 4 weeks. Replacement of appropriate hormones may be required as the steroid dose is tapered.
- **Hepatic:**
 - For **Grade 3** events, monitor liver function tests more frequently until returned to baseline values (consider weekly).
 - Treat with IV or oral corticosteroids
 - For **Grade 4** events, treat with intravenous corticosteroids for 24 to 48 hours (or longer if clinically indicated). Monitor LFTs labs at least weekly until Grade 0-1 or baseline at Investigator discretion.
 - When symptoms improve to Grade 2 or less, a steroid taper should be started and continued over no less than 4 weeks.
 - Hold drug if an elevated AST or ALT lab value that is $\geq 5X$ the upper limit of normal (ULN) **and** an elevated total bilirubin lab value that is $\geq 2X$ the ULN **and**, at the same time, an alkaline phosphatase lab value that is $< 2X$ the ULN, as determined by way of protocol-specified laboratory testing or unscheduled laboratory testing.* Monitor labs tests more frequently until AST, ALT and total bilirubin values return to baseline or $<$ grade 3.

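### The AST/ALT hold, steroid, resume and stop rules disagree, partly within Section 10 itself, and the Grade 4 exception in Table 10.2 points to a footnote that covers only Grade 3

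*Combined protocol and SAP*

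**What the plan says.** AST/ALT management appears in four places in the protocol.

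- **Section 10.1.** "Drug-related grade 4 toxicities will require subject to discontinue all study treatment". No exception is given.
- **Section 10.2, Table 10.2.** Grade 3 AST/ALT: withhold and give corticosteroids. Grade 4: "Permanently discontinue --see exception below", with marker 2. Footnote 2 opens "For grade 3 liver toxicity with elevated AST and/or ALT". It then notes that HCC patients may start with Grade 1-2 elevation and continues: "if these patients have Grade 3 elevation of AST/ALT, hold therapy and resume treatment when AST/ALT return to baseline or Grade" 1 or lower. It takes the patient off study if AST/ALT is not back to baseline or below 5x ULN within 12 weeks of the start of Grade 3. General instruction 2, above the table, allows resumption at Grade 0-1 after steroid taper. It stops the drug permanently if the event has not resolved within 12 weeks of the last dose.
- **Section 9.1.4.** The general irAE paragraph asks for recovery to Grade 1 or less ("or to Grade 2 for ALT or AST") within 12 weeks, counted for AST/ALT from the start of Grade 3. If that fails, discontinuation is to be considered, at discretion. The hepatitis text says "Treatment should be interrupted when transaminase or alkaline phosphatase increases are accompanied by Grade 3 total bilirubin, and/or Grade 3 coagulation tests", or when the patient has symptoms. For Grade 3-4 AST/ALT with a normal baseline, or above 3x baseline if the patient began above 2x ULN, it adds "and no other underlying etiology is found, consider treatment with intravenous corticosteroids".
- **Appendix I, Hepatic.** "Hold drug if an elevated AST or ALT lab value that is" at least 5x ULN, together with bilirubin of at least 2x ULN and alkaline phosphatase below 2x ULN.

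**The concern.** A site with a raised AST or ALT has to decide four things: whether to hold, whether to give steroids, when to resume and when to stop for good. The texts do not give one answer to each. Two of the disagreements lie wholly inside Section 10, so reading Section 10 first does not settle them.

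The event is one the protocol itself leads the reader to expect. Section 1.1 cites an earlier PD-1 study in HCC with Grade 3-4 AST increase in 12% and ALT increase in 10%, and eligibility admits AST and ALT up to 5x ULN. Patient safety is the main stake. Consistency of the safety data is the second. Section 3.1 lists treatment-related adverse events as a primary endpoint. The toxicity stopping guideline in Section 17.2.2 excludes reversible liver-test elevation and counts Grade 3 or higher elevation once it lasts 12 weeks. Holding and steroid use can affect how long an elevation lasts, and so whether it is counted.

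**Working it through.** There is no stated figure to reproduce. The check applies each text to the same liver result, using current text only.

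Assumption: Grade 3 AST/ALT begins above 5x ULN. The protocol adopts CTCAE without reproducing its limits, but footnote 2's recovery line fits this. Step 2 needs only that Grade 1 ends below 5x ULN.

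**1. Grade 4 AST/ALT, drug-related.** Section 10.1: discontinue. Table 10.2: discontinue, with an exception at marker 2. Footnote 2: Grade 3 only, and that row already says withhold. The exception has no content.

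**2. Grade 1 at baseline, rises to Grade 3, held; at 12 weeks Grade 2 and below 5x ULN.**

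| Text | Line | Met? | Result |
|---|---|---|---|
| Footnote 2, resume | baseline or Grade 1 or less | no | may not resume |
| Footnote 2, withdraw | baseline or below 5x ULN, 12 weeks from start of Grade 3 | yes | need not be withdrawn |
| General instruction 2 | resolved within 12 weeks of last dose | no, if resolved means Grade 0-1 | permanent discontinuation |
| Section 9.1.4 | Grade 2 suffices, 12 weeks from start of Grade 3 | yes | counts as recovered; failure would only prompt consideration of stopping |

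General instruction 2 does not define resolution. I read it as Grade 0-1, the level in its preceding sentence. Section 15.4 has a looser definition for event reporting that includes stabilisation as a chronic event. If a site used that one, the third row could change.

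Clocks: the difference between the two deadlines equals the time from last dose to start of Grade 3. Suppose no dose is missed and Grade 3 is first seen at the next pre-dose visit, 21 days later, or 21 + 3 = 24 days with the visit window. Twelve weeks is 12 x 7 = 84 days.
- General instruction 2: day 84 after the last dose.
- Footnote 2: day 21 + 84 = 105, or 24 + 84 = 108.
- Difference: 0 (Grade 3 straight after a dose) to about 24 days.

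**3. Steroids at Grade 3.** Table 10.2 says to administer them. Section 9.1.4 says to consider them once other causes are excluded. For a patient who starts at 4x ULN, the 9.1.4 threshold is 3 x 4 = 12x ULN. At 8x ULN the table orders steroids and the 9.1.4 threshold is not reached. Section 10.2.1, also within Section 10, makes steroids optional for an ALT rise of fivefold or more from a normal baseline, after viral flare and other causes are ruled out.

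**4. Isolated Grade 3 AST/ALT, normal bilirubin and coagulation, no symptoms.** Table 10.2: withhold. The 9.1.4 interruption sentence and the Appendix I hold bullet describe combined criteria that this patient does not meet, so neither speaks to the case.

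**How many patients.** If the cited rates carried over to 28 evaluable patients: AST 0.12 x 28 = 3.4; ALT 0.10 x 28 = 2.8. With full overlap about 3 patients reach Grade 3 or 4. With none, (0.12 + 0.10) x 28 = 6.2, about 6. The documents do not show how many would fall in the week-12 gap.

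**The case against.** The best defence is that Section 10 is the dosing section. Section 8.4 sends the reader there for dose modification, and Section 10.2 words its table as mandatory. Appendix I presents its measures as suggestions, and its note describes the hepatic criteria as a level that may call for further work-up. Section 9.1.4 is drug information. This largely stands for the hold trigger. A reader might infer three rival triggers, so that an isolated Grade 3 rise would be dosed under 9.1.4 or Appendix I. The documents do not support that: those sentences say when and if, not only when or only if, and neither says to continue. What remains is that no sentence gives Section 10 precedence, while 9.1.4 and 10.2 both refer the reader to Appendix I.

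Other points also have force:
- Section 10.1 answers the Grade 4 question, and footnote 2 gives no Grade 4 permission. A careful reader would stop treatment. The table still announces an exception, and the documents do not say what it was meant to be.
- Footnote 2's two lines serve different decisions, and its withdrawal line and clock broadly match 9.1.4. It could also be read as the specific rule that displaces general instruction 2. It does not say so, and its own gap remains.
- The level of 3x baseline in 9.1.4 (6.3x to 15x ULN for baselines of 2.1x to 5x) might be taken as a rival hold level. It is a threshold for considering steroids and measures no conflict over dosing.
- The week-12 gap might be extended to patients with a normal baseline. Footnote 2 most naturally addresses those elevated at entry, so general instruction 2 would stand alone for the others.
- A reader might infer an effect on who can be scored for disease control. Section 3.1.1 asks only for eligibility, measurable disease, one dose and one post-baseline assessment.
- The 12% and 10% come from a different PD-1 antibody at 0.1-10 mg/kg.

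**Conclusion.** The point holds as a set of contradictions that should be fixed. It does not undermine the design or the primary efficacy analysis.

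Firm, and internal to Section 10: the Grade 4 exception with no content, and the different stopping lines and clocks in footnote 2 and general instruction 2. Firm across sections: mandatory stopping against stopping to be considered, and steroids to be given against steroids to be considered on a partly baseline-based threshold. Weaker: the hold trigger, where the texts can coexist and only a statement of precedence is missing.

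In size, about three to six of 28 patients would reach Grade 3-4 AST/ALT if the cited rates applied, and the clocks differ by 0 to about 24 days under the visit assumptions above. No effect on a trial result can be quantified from the documents. The week-12 conflict with general instruction 2 rests on reading resolution as Grade 0-1. I take no view on which clinical rule is right.

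**What to change.** The sponsor's clinical team should reconcile these texts and state one AST/ALT rule once, in Table 10.2. It should cover the hold trigger, the steroid trigger, the line for resuming, the line for stopping and a single starting point for the 12-week clock. It should say what applies to patients elevated at entry and what resolution means. Footnote 2's marker and the grade it describes should agree with each other and with Section 10.1. The AST/ALT hold, treat and recover sentences in Section 9.1.4 and Appendix I should become a pointer to Table 10.2, and Section 10.2.1 should be checked against it. The choice of rule is the clinical team's.

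The cost is a wording amendment and a memo to the site. No visits, tests or patients are added.

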10.2.1 Hepatic Toxicity

At baseline, all subjects should be assessed for HBsAg, HBsAb, anti-HBc antibody, HBeAg, and anti-HCV. Patients who test negative for these hepatitis labs do not need to repeat these lab tests again, unless clinically indicated. Evidence of prior HBV should also prompt a viral load measurement at baseline. A viral load <100 IU/mL is required for study entry. Those with active HBV must have been treated with antiviral therapy for ≥3 months before initiation of study treatment. Subjects with controlled HBV on therapy should stay on this therapy throughout pembrolizumab. Subjects who are positive for HBsAg, or anti-HBc (but negative for HBsAg and HBV DNA), should be assessed for viral loads, anti-HBs, anti-HBc and HBsAg every 3 weeks (Q3W), independent of treatment delays.

Viral loads and HBsAg should also be assessed if there is an elevation in ALT >3× baseline, a tenfold or greater increase in HBV or HCV DNA over baseline, or an absolute increase in HBV or HCV DNA over 10⁵ c/mL. **If evidence of reactivation is present, the Sponsor should be consulted within 24 hours, and pembrolizumab treatment should be interrupted.**

If there is a 5X or greater elevation in ALT (if normal at baseline), workup should be undertaken to rule out SBP, obstruction, medication, or vascular injury. If these are unrevealing, consideration of pembrolizumab toxicity should be undertaken. Steroids may be considered if viral flare and other etiologies are ruled out.

Table 1: Hepatitis Treatment Guidelines

Test(s)	Patient Status	Included in KN-0224	Any HBV Treatment Needed?
HBsAg (-) Total anti-HBc (+) Anti-HBs (+)	Immune after natural infection	YES	NO
HBsAg (-) Total anti-HBc (-) Anti-HBs (+)	Immune after vaccination	YES	NO
HBsAg (+) Total anti-HBc (+) IgM anti-HBc (+) Anti-HBs (-)	Acute Infection	NO	--
HBsAg (+) Total anti-HBc (+) IgM anti-HBc (-) Anti-HBs (-)	Chronic Infection	YES	YES, need to be on a NI for at for at least 12 week prior to start of Pembro without evidence of a flare

			during that period (ie, has been on chronic NI therapy) EXCLUDE IF: (a) <12 weeks of therapy; (b) HBV DNA not under control during this time frame; (c) Documented HBV flare in the past 12 weeks
HBsAg (-) Total anti-HBc (+) IgM anti-HBc (-) Anti-HBs (-) HBV DNA (negative)	Unclear. Could be: (1) Resolved infection (most common) (2) False positive anti-HBc (so actually NOT HBV infected) (3) Low Level infection (4) Resolving Acute infection	YES	NO
HBsAg (-) Total anti-HBc (+) IgM anti-HBc (-) Anti-HBs (-) HBV DNA (+)	(5) Low Level infection (6) Resolving Acute infection	YES	YES (as above)

